Evolocumab in Acute Coronary Syndrome

NCT03515304

6/5/2020

Date: 6/5/2020

Principal Investigator: [name]

Application Number: IRB00156313

JHM IRB - eForm A – Protocol

- Use the section headings to write the JHM IRB eForm A, inserting the appropriate material in each. If a section is not applicable, leave heading in and insert N/A.
- When submitting JHM IRB eForm A (new or revised), enter the date submitted to the field at the top of JHM IRB eForm A.

1. Abstract

- a. Provide no more than a one page research abstract briefly stating the problem, the research hypothesis, and the importance of the research.

Despite aggressive early intervention and current secondary prevention strategies, hundreds of thousands of patients who survive hospitalization for acute coronary syndrome (ACS) experience subsequent unfavorable outcomes, including recurrent ischemic events and unfavorable cardiac remodeling associated with progressive left ventricular dysfunction and congestive heart failure. Vascular and myocardial inflammation are significantly increased in ACS patients, are closely correlated to LDL-C levels, and are associated with these adverse consequences in the post-ACS patient population. Inflammation may also play a role in platelet aggregation one of the responsible mechanisms for the index and for any recurrent coronary thrombotic events. Serum proprotein convertase subtilisin/kerin type 9 (PCSK9) levels are also increased in ACS, may raise LDL-C, and our pre-clinical studies indicate that PCSK9 is also a potent inducer of vascular inflammation. The addition of the PCSK9 antibody evolocumab, currently approved to lower LDL-C in certain patient populations, to current medical therapies would appear to be of particular benefit in an important subset of ACS patients, those with non-ST-elevation myocardial infarction (NSTEMI) by markedly reducing LCL-C, stabilizing vulnerable plaque, and limiting inflammation-associated myocardial cell loss and resultant dysfunction.

Hypothesis: In a placebo-controlled, randomized double blind trial, the addition of evolocumab to standard care in NSTEMI patients (1) decreases LDL-C during hospitalization and at 30 days, (2) decreases vascular/plaque and myocardial inflammation as assessed by PET scanning at 30 days, and improves (3) serum markers of endothelial function and of platelet function at hospital discharge and at 30 days, and (4) echocardiographic assessment of left ventricular function at 30 days and six months.

This is the first PCSK9 inhibitor trial which examines these outcomes in the ACS patient population. It will provide valuable data on the extent and time course of LDL-C reduction as well as the impact of inhibition on inflammatory markers and on imaging assessment of vascular and myocardial inflammation, all of which may significantly impact important clinical outcomes in this high risk patient cohort.[1]

2. **Objectives** (include all primary and secondary objectives): To conduct a placebo-controlled randomized, double blind study of the effect of the addition of evolocumab to standard care in NSTEMI patients

2.1 Primary

The primary objective is the difference in the mean % change in LDL-C from baseline to 30 days in the evolocumab and placebo groups.

2.2 Secondary

The secondary objectives are to compare in the evolocumab and placebo groups:

- a. Serial serum markers of inflammation, lipids, myocardial injury, and of left ventricular function will be collected at baseline, day 1, day 3, at hospital discharge and at 30 days follow up.

The time points of comparison are day 3, hospital discharge and 30 days.

- i. PCSK-9
- ii. Soluble LOX-1
- iii. Interleukin-6
- iv. High sensitivity C-reactive protein
- v. HDL-cholesterol
- vi. Triglyceride
- vii. Total cholesterol
- viii. Troponin
- ix. Pro-BNP

- b. The change between early hospitalization or shortly following discharge and thirty day assessments of

- i. PET-FDG assessed vascular inflammation in the most diseased segment of aorta or carotid artery
- ii. Echo assessed regional wall motion in the infarct territory
- iii. Echo assessed global LV function
- iv. Echo assessed LV systolic and diastolic volumes

- c. At thirty days:

- i. Comparison of PET-FDG assessment of vascular inflammation in the evolocumab versus placebo group as described in 2.2. b i
- ii. Echo assessed as described in 2.2. b ii-iv
- iii. Angina class
- iv. New York Heart Association functional class
- v. LDL-C and serum markers as described in 2.2. a
- vi. Determine the relationship if any among the extent of change in the serum makers, FDG-PET results and echocardiogram results.

- d. At six months

- i. Angina class
- ii. New York Heart Association functional class
- iii. LDL-C and serum markers as described in 2.2. a
- iv. Echo assessment as described in 2.2. b ii-iv

- e. At 12 months
Serum markers as described in 2.2 a

2.3 Exploratory

- a. The exploratory basic science outcome is: Direct comparison of endothelial cell function in cells harvested from intravascular equipment in the evolocumab- and placebo-randomized patient groups.
- b. The exploratory imaging outcome is: To assess changes in FDG-PET-guided myocardial inflammation in the evolocumab and placebo groups at thirty days. Additionally, we will compare PET assessed vascular inflammation in the evolocumab and placebo groups on the exam obtained during the early hospitalization.
- c. Platelet aggregation and function studies.

3. Background (briefly describe pre-clinical and clinical data, current experience with procedures, drug or device, and any other relevant information to justify the research)

The total burden of coronary heart disease and associated mortality have decreased over the last 10 years. Although the incidence of STEMI has decreased by 50% to 60% over the last decade [2], the proportion of patients with acute coronary syndrome who now present with NSTEMI has grown substantially and now represents approximately 70% of all acute coronary syndrome patients [3]. This shift is likely multifactorial, but relates to the aging population, an increase in diabetes mellitus, and perhaps a change in plaque characteristics with fewer of the plaque rupture events associated with STEMI [4]. Recent studies show that over the last decade the NSTEMI population is getting older with an increased prevalence of diabetes, hypertension, lung disease, chronic renal disease, and prior coronary revascularizations [5]. Acute myocardial infarction remains a major cause of morbidity and mortality in the United States, Europe and Asia [6]. Despite the majority of NSTEMI patients receiving guideline recommended dual antiplatelet, beta blocker, ACE or ARB and statin therapies in addition to coronary revascularization, in hospital mortality is 5% and six-month mortality in NSTEMI hospital survivors is 7.6% (*IBID*). Six-month mortality remains above 10% in hospital survivors with elevated baseline risk, such as advanced age and evidence of heart failure on admission (*IBID*). Long term mortality and recurrent ischemic events also remain high in NSTEMI patients [7]. Recurrent ischemic events are likely related to inflammation and the degree of residual coronary plaque burden. The Providing Regional Observations to Study Predictors of Events in the Coronary Tree (PROSPECT) study evaluated the risk for recurrent ischemic events using three vessel intracoronary ultrasound in patients receiving percutaneous coronary intervention for acute coronary syndrome [8]. During the three-year follow-up, with guideline directed risk factor modification, recurrent ischemic events were highest in patients with lesions described as thin fibrous cap atheroma, plaque burden $\geq 70\%$, and minimal luminal area $\leq 4.0 \text{ mm}^2$. Additionally, patients with elevated markers of inflammation (hsCRP) at six months experienced higher rates of recurrent ischemic events at follow-up. Although the number of high risk thin-cap fibroatheroma did not differ between the high-hsCRP and normal-hsCRP groups, nonculprit lesion-related ischemic events were independently predicted by an elevated hsCRP. These data indicate that inflammation increases the likelihood of vulnerable plaque rupture with result ant ischemic events [9]. These data suggest that despite aggressive risk factor modification in patients with acute coronary syndrome, recurrent ischemic events are frequent and are associated with non-culprit lesion plaque burden and ongoing inflammation.

In addition to recurrent ischemic events, heart failure is common post myocardial infarction and a leading cause of death in older NSTEMI patients. In a large cohort of patients 65 years of age and

older suffering a first myocardial infarction, new heart failure was diagnosed in 37% during the index hospitalization (13% mortality) with an additional 71% of hospital survivors developing heart failure during the five-year follow up period, 64% of which occurred in the first year. Short- and long- term mortality are significantly greater in those NSTEMI patients who develop heart failure [10]. Inflammatory mediators are also activated in heart failure after myocardial injury and are associated with progressive left ventricular dysfunction [11].

Evolocumab is a monoclonal antibody that inhibits PCSK9 and is FDA-approved as an adjunct to diet and maximally tolerated statins for use in certain patients who need to further significantly lower LDL-cholesterol level. In a large randomized clinical trial in patients with atherosclerotic cardiovascular disease (median of 3 years after a recent event) and LDL cholesterol levels of 70 mg per deciliter or higher who were receiving statin therapy, the addition of evolocumab significantly reduced the risk of cardiovascular death, myocardial infarction, stroke, hospitalization for unstable angina, or coronary revascularization during a median follow-up of 2.2 years [12]. In this study, the median LDL cholesterol on statin therapy was 92 mg / dL and the addition of evolocumab reduced LDL cholesterol by 59% to a median of 30 mg / dL. Little is known regarding other potential additional benefits of PCSK9 inhibition in the setting of ACS.

ACS is associated with a marked increase of serum PCSK9 that likely has an important pathophysiologic role in mediating vascular and myocardial inflammation, leading to plaque vulnerability of both culprit and non-culprit coronary vessels as well as adverse myocardial remodeling and resulting contractile dysfunction. Growing evidence emphasizes a potential role of PCSK9 antibodies beyond their LDL-cholesterol lowering capacity (pleiotropic effects), which are likely beneficial in managing NSTEMI [13]. The Ottawa Heart Genomics Study and the Emory Cardiovascular Biobank both demonstrated an association between elevated PCSK9 levels and adverse acute and long-term events in patients with ACS. PCSK9 levels are markedly elevated during an ACS, and in one study were related to the composite endpoint of death and recurrent ACS at 1-year follow-up.[14] Additional data indicate that elevated PCSK9 adversely affects coronary plaques through several pathways, including pro-inflammatory LDL oxidation and direct modification of plaque composition [15-17]. Additionally, chronically elevated PCSK9 levels are associated with progression of atherosclerosis [14]. Finally, a recent study suggests that increased PCSK9 levels are associated with higher platelet reactivity and are a possible predictor of ischemic events in ACS patients [18].

Over the past few decades, our understanding of the vascular biology of atherogenesis and its clinical presentations has advanced significantly. It is now apparent that inflammatory processes play a key role not only in the initiation and progression of ASCVD but also in the clinical events associated with instability of already established atherosclerotic plaques [19-21]. Traditional and novel cardiovascular risk factors trigger a chronic inflammatory process, which is accompanied by loss of vasodilatory and antithrombotic properties of the vascular endothelium [22-24]. Clinical studies show that this emerging biology of inflammation in atherosclerosis applies directly to human pathology [25]. Elevated inflammatory markers predict outcomes of ACS patients independently of the extent of myocardial damage [25]. In addition, low-grade chronic inflammation, as indicated by levels of the inflammatory marker hsCRP, prospectively independently defines risk of atherosclerotic complications, thus adding to the prognostic information provided by traditional risk factors [26, 27]. Moreover, certain treatments that reduce coronary risk also limit inflammation [28, 29].

Identifying reliable endothelial cell (EC) function markers for *in vivo* testing remains a challenge. In this clinical trial, we propose to utilize the emerging EC function marker sLOX1. The LOX1 receptor is an endothelial receptor for atherogenic oxidized-LDL and is implicated in the

pathogenesis of atherosclerosis [30]. In addition, nuclear imaging studies detecting radiolabeled LOX1 report significantly higher accumulation of LOX1 in grade IV atheroma than in more stable lesions [31]. It was recently reported that LOX1 is converted to soluble molecules by proteolytic cleavage at the membrane proximal site of the extracellular domain. In the same study, EC activation by pro-inflammatory stimuli, e.g. TNF-a, led to cell-surface expression of LOX-1 which precedes soluble LOX-1 production [32]. sLOX1 is also proposed as a marker of plaque instability in ACS patients [33]. Finally, persistently elevated sLOX1 levels in ACS patients are linked to adverse clinical outcomes [34]. Based on the scientific evidence, we believe that sLOX1 is a suitable marker for endothelial dysfunction and possibly plaque instability in the setting of ACS and NSTEMI.

In this pilot study, we will utilize non-invasive PET imaging to assess vascular/plaque and myocardial inflammation. A recent review article nicely summarizes the utility of PET in the setting of ACS [35]. The strength of PET-guided imaging in this setting is the identification of activated inflammatory cells in the atherosclerotic plaque, providing important information regarding the mechanism of vascular instability. Furthermore, longitudinal PET studies can assess the effectiveness of novel anti-inflammatory therapies, such as evolocumab. Initial validation of FDG-PET imaging in the setting of ACS was performed in mice [36], but other reports also provide proof of feasibility in large animals and humans [37, 38]. Ripschler et al. subsequently demonstrated that the extent of FDG-derived myocardial inflammation early after myocardial infarction correlated with infarct size and systemic inflammatory markers at that time and with LVEF and cardiac volumes at 6-9 month follow-up [39].

The multimodality dal-PLAQUE imaging study successfully utilized FDG-PET to assess plaque inflammation and burden in patients with high risk of coronary heart disease [40]. A subsequent study reported a functional alteration of the plaque, characterized by activation of resident inflammatory cells, which can cause plaque instability and occlusive thrombus formation [41]. Since persistent activation of adaptive immunity in patients with unstable angina is linked to coronary instability [42], we propose to evaluate the impact of evolocumab on the extent and degree of vascular inflammation in our study cohort.

4. Study Procedures

- a. Study design, including the sequence and timing of study procedures (distinguish research procedures from those that are part of routine care).**

This is a phase 2, double-blind, randomized, placebo controlled clinical trial of 420 mg evolocumab administered subcutaneously using an autoinjector/pen in NSTEMI patients during early hospitalization at the Johns Hopkins Hospital or the Johns Hopkins Bayview Medical Center.. The placebo and evolocumab will be given exactly the same way with the same Amgen provided device. All participants will receive standard care for NSTEMI, including high dose statin, aspirin, beta blocker, and, as appropriate, ACE-I or ARB and early intervention. High dose statin therapy consists of atorvastatin 40mg or 80mg or rosuvastatin 20mg or 40mg per the most recent ACC/AHA guidelines. [43] After signing informed consent, subjects will be randomized to receive one dose of evolocumab or matching placebo subcutaneously. Research blood samples for LDL-C and inflammatory markers, and PET imaging assessment of vascular inflammation as well as echocardiographic studies for left ventricular function will be obtained. An independent Data and Safety Monitoring Committee will review all potential side effects and clinical outcomes during the twelve months of follow-up.

At the 30-day follow-up visit we will perform a physical exam and obtain a history of any clinical events including adverse events. We will perform a second FDG-PET study to assess vascular and myocardial; inflammation. Additionally, we will assess LDL-C and serum markers of inflammation and endothelial function as outlined in 2.2 a.

At the 6-month follow-up visit will perform a physical exam and obtain a history of any clinical events including adverse events. Additionally, we will assess LDL-C and serum markers of inflammation and endothelial function as outlined in 2.2 a.

At the 9-month follow-up visit, we will contact the participant by phone to learn of any adverse events. If the participant was admitted to the Emergency Department or Hospital we will obtain permission to obtain medical records.

At 12-month follow-up visit we will assess lipid profile and serum markers of inflammation and endothelial function as outlined in 2.2 a.

All above are research studies with the exception of the clinical echocardiogram during the initial hospitalization.

b. Study duration and number of study visits required of research participants.

The study duration for each participant is twelve-months and there are three study visits required.

c. Blinding, including justification for blinding or not blinding the trial, if applicable.

The investigators and participants are blinded. Blinding is necessary to avoid potential bias in data gathering and analysis. The Hopkins Investigational Pharmacy will have access to study drug assignment if there is a clinical need for the subjects' treating physician to be aware of assignment.

d. Justification of why participants will not receive routine care or will have current therapy stopped.

All participants will receive routine care and will not have current therapy stopped. Evolocumab is not standard of care for ACS or NSTEMI patients.

e. Justification for inclusion of a placebo or non-treatment group.

Inclusion of a placebo, comparator group is necessary to best determine the safety and efficacy of evolocumab in NSTEMI patients. As noted above, evolocumab is not considered "treatment" for this patient population and hence we do not believe there is a "non-treatment" group, or ethical concern by inclusion of a placebo group.

f. Definition of treatment failure or participant removal criteria.

Early stopping rules:

Only participants who go to CABG (unanticipated) will be removed, because procedures utilizing the heart and lung machine itself are associated with markedly increased inflammation.

- a. Description of what happens to participants receiving therapy when study ends or if a participant's participation in the study ends prematurely.

Participants will only receive one dose of the study drug and will not receive any additional study related therapy.

5. Inclusion/Exclusion Criteria

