5.2 Exclusion Criteria

- a. STEMI
- b. Patients requiring invasive support because of compromised hemodynamics.
- c. Scheduled for cardiac surgery.
- d. Current or prior treatment with a PCSK9 antibody.
- e. Current participation in an intervention clinical trial.
- g. Female of childbearing potential. This is a female subject who has not used acceptable method(s) of birth control (see below) for at least one month prior to screening, unless the subject is sterilized or postmenopausal. Menopause is defined as: 12 months of spontaneous and continuous amenorrhea in a female \geq 55 year of age.
 - Acceptable method(s) of birth control definition: One highly effective method (methods that can achieve a failure rate of less than 1% per year when used consistently and correctly)
 - Combined hormonal (estrogen and progestogen) contraception associated with inhibition of ovulation (oral, intravaginal, transdermal)
 - Progestogen-only hormonal contraception associated with inhibition of ovulation (oral, injectable, implantable)
 - Intrauterine device (IUD)
 - Intrauterine hormone-releasing system (IUS)
 - Bilateral tubal occlusion
 - Vasectomized partner
 - Sexual abstinence
 - h. Contraindication to statin therapy.
 - i. Subject likely not to be available to complete all protocol-related study visits or procedures.
 - j. Latex allergy
 - k. History of severe hypersensitivity to any monoclonal antibody.

6. Drugs/ Substances/ Devices

- a. The rationale for choosing the drug and dose or for choosing the device to be used.

The drug evolocumab was chosen because of studies indicating that it reduces inflammation and improves lipid profile in patients already on statin therapy. [12] The dose was chosen based on

that approved by the FDA for clinical use in patients with stable coronary disease, available in the United States and reduces LDL cholesterol. [44]

- b. Justification and safety information if FDA approved drugs will be administered for non-FDA approved indications or if doses or routes of administration or participant populations are changed.

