Evolocumab is an FDA approved medication that will be administered for a non-FDA approved indication, hospitalized patients with NSTEMI. This is justified based on clinical and pre-clinical data indicating that vascular and myocardial inflammation is increased in NSTEMI patients, that inflammation is associated with adverse outcomes in this patient group, that in stable CAD patients, anti-inflammatory interventions improve outcomes, and that evolocumab has anti-inflammatory properties. The dose and route of administration are the same as that administered for FDA approved indications.

We are applying for an exemption from the FDA such that an IND is not needed for the proposed mechanistic study in NSTEMI patients. Safety information on the use of these drugs is detailed above.

An IND exemption request will be submitted to the FDA.

7. Study Statistics

- a. Primary outcome variable.

The primary outcome will assess the difference of LDL-C serum concentration between the placebo and evolocumab groups at 30 days. To assess the primary endpoint of the mean percent change from baseline in LDL-C at day 30, a repeated measures linear effects model will be used in comparing the efficacy of evolocumab vs placebo.

- b. Secondary outcome variables.

For the secondary outcome of comparing the changes in target to background ratio (TBR) over time (30-day FDG PET scan minus early hospitalization or shortly following discharge FDG PET scan) between the groups, the following statistical approach will be used consistent with the prior literature.[45] Specifically, difference in the percent change in TBR at 30 days from early hospitalization (30 day – early hospitalization TBR) between the two randomized groups will be compared with ANCOVA using the baseline TBR as a covariate. The percent difference between the index vessel MDS TBR in the placebo and evolocumab groups at 30 days will be analyzed using Kruskal Walis testing.

The non-parametric biomarkers of the secondary endpoint will be log transformed, and the results interpreted as the difference in geometric means between the groups. The analysis will be performed in the primary evaluable population, defined as data from subjects that provided imaging/laboratory data at the indicated time points.

A one-sided p-value ≤ 0.05 will be considered significant, based on the assumption that evolocumab will reduce, and not increase, inflammation.

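### Section 4.f removes patients who go to unanticipated CABG without saying from what; on its natural reading this is a post-randomization exclusion that can lose 30-day LDL-C values and scheduled safety follow-up

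*Combined protocol and SAP*

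**What the plan says.** Section 4.f, on treatment failure and participant removal, has one rule: "Only participants who go to CABG (unanticipated) will be removed". The reason follows: "because procedures utilizing the heart and lung machine itself are associated with markedly increased inflammation". The next item, on participation that ends early, covers study therapy only. It says nothing about visits or data.

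The other relevant places are:

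- **Section 5.2** excludes at entry patients "Scheduled for cardiac surgery".
- **Section 2.1** makes the primary objective the "difference in the mean % change in LDL-C from baseline to 30 days". Section 7.a analyses it with a repeated measures model.
- **Section 7.b**, under secondary outcomes, defines the only analysis population in the document: "defined as data from subjects that provided imaging/laboratory data at the indicated time points".
- **Section 4.a** says an independent committee "will review all potential side effects and clinical outcomes during the twelve months of follow-up". Adverse events are collected at the 30-day and 6-month visits, and at nine months "we will contact the participant by phone to learn of any adverse events".
- **Section 4.e** says the placebo group is "necessary to best determine the safety and efficacy of evolocumab in NSTEMI patients".
- **Section 8.c** sends clinically significant unanticipated problems to the DSMB and the IRB.

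**The concern.** Scheduled surgery is screened out at entry, and section 4.a places randomization after consent. The rule in 4.f is therefore triggered by a clinical event during the study. Only one dose is given, so there is no further study treatment to stop. The natural meaning of removal is then removal from follow-up, from analysis, or from both.

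The reason given is narrower than the rule. Inflammation from the heart-lung machine may justify setting aside PET and inflammatory-marker values taken after surgery. It does not by itself justify losing LDL-C, which is the primary endpoint, or adverse-event data.

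Two things are at stake. The first is whether the 30-day LDL-C comparison remains a comparison of the groups as randomized. The second is whether scheduled safety follow-up is complete for patients with a serious clinical course, in a trial that says its placebo arm serves safety as well as efficacy.

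**Working it through.** **Step 1. What each reading of the rule would lose**

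| Meaning of removal | 30-day LDL-C if CABG precedes day 30 | Later scheduled contacts |
|---|---|---|
| From visits and analysis | lost | lost |
| From analysis only | lost | could continue |
| From visits only | lost; earlier LDL-C values could stay in the model | lost |
| From inflammation endpoints only | kept | kept |

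The document does not choose among these. Only the last fits the stated reason. None of the first three can be squared with both the primary objective and the twelve-month review.

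**Step 2. The plan's own power figure**

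Inputs are from section 7.c: 30 per arm, one-sided 0.05, two-sample comparison (noncentral t).

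- Percent change (Table 2): -50 (SD 12) against -75 (SD 14), a difference of 25 points. Pooled SD = √((12² + 14²)/2) = 13.04. Power is above 99.99%.
- Day-30 LDL-C: 55 (40-70) against 28 (14-42) mg/dL, a difference of 27. SDs implied by the interquartile ranges are 30/1.349 = 22.2 and 28/1.349 = 20.8. Power is 99.9%.

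Both agree with the 99+% in Table 1.

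**Step 3. Number removed (assumption)**

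No CABG rate is given. Assuming 5-15% of 60: 0.05 × 60 = 3 and 0.15 × 60 = 9.

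**Step 4. Shift in the primary estimate**

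Shift in an arm's mean = share of that arm removed × difference in percent LDL-C change between removed and retained patients. The difference is also an assumption.

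- Difference of 10 points, 5-15% of one arm removed: 0.05 × 10 = 0.5 to 0.15 × 10 = 1.5 points.
- Extreme case, all nine from one arm: 9/30 × 10 = 3.0 points.
- Equal removal of similar patients from both arms: 1.5 - 1.5 = 0.
- Larger assumed differences, 10% of one arm removed: 0.10 × 25 = 2.5 and 0.10 × 50 = 5.0 points.
- To erase the planned 25 points with nine removed from one arm, they would have to differ by 25/0.30 = 83 points.

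**Step 5. Power after removal**

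- Percent-change scale: above 99.99% at 28, 25 and 24 per arm and at 30 vs 21. It is still above 99.99% at 30 vs 21 with the difference cut to 25 - 3 = 22 points.
- Interquartile-range SDs, 27 mg/dL: 99.9% at 28 per arm, 99.7% at 25, 99.6% at 24, and 99.6% at 30 vs 21.
- The same SDs with the extreme shift: 3% of the baseline 110 is 3.3 mg/dL, so the difference is 27 - 3.3 = 23.7. At 30 vs 21, power is 98.4%.

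**Step 6. Scheduled adverse-event contacts**

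Section 4.a gives three per patient (30 days, 6 months, 9 months), so 60 × 3 = 180. If removal ends follow-up, the losses are:

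| Timing of CABG | 3 patients | 9 patients |
|---|---|---|
| Before day 30 | 3 × 3 = 9 | 9 × 3 = 27 |
| Day 30 to 6 months | 3 × 2 = 6 | 9 × 2 = 18 |
| 6 to 9 months | 3 × 1 = 3 | 9 × 1 = 9 |

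In the last two rows the 30-day LDL-C has already been drawn. The 12-month visit would also be lost, but section 4.a describes it as blood sampling only, so it is not counted. The evaluations after injection in section 8.b have no stated schedule and are not counted either.

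**The case against.** The best defence is that nothing in 4.f says visits stop or data are discarded. Section 4.a makes no exception for CABG, so the two sections together could mean that safety follow-up continues and only inflammation-dependent analyses are restricted. That is possible, and it means the losses above are inferences from an undefined word. But 4.f does not say so, no section keeps these patients in LDL-C collection or in an as-randomized set, and staff applying the sentence literally would end participation.

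A reader might infer that the evaluable population in 7.b also drops these patients from the primary analysis. The documents do not support that. The definition sits under secondary outcomes, and the primary has its own repeated measures model, which could use pre-CABG LDL-C values if they are kept. Whether they are kept is not stated.

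A reader might also infer that the CABG itself goes unreported. Section 8.c still covers clinically significant unanticipated problems, plausibly including the operation. What is at risk is scheduled follow-up after removal.

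Blinding of investigators and participants (4.c) limits removal that depends on arm, so the extreme case of nine from one arm is unlikely. Blinding does not stop the event itself from being related to treatment or prognosis, nor prevent a chance imbalance in small counts.

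Finally, LDL-C measured after surgery may be affected by it. The documents do not show otherwise, and the Abstract links inflammation to LDL-C in ACS. This supports a sensitivity analysis, but it is not the reason 4.f gives for removal.

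**Conclusion.** The point holds as a defect in the removal rule. The rule is unlimited in scope, its reason covers only inflammation, and its natural reading is a post-randomization exclusion that sections 4.a and 4.e do not accommodate. The passages must be reconciled.

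The size is modest and rests on assumptions. With 3-9 removals and a 10-point LDL-C difference, the primary estimate moves by 0 to 3.0 points against a planned 25, and 3-27 of 180 adverse-event contacts could be lost if CABG occurs within nine months. It would be tempting to conclude that the trial loses power or that its primary result could be overturned. The figures do not support this: power stays at about 98% or higher in the extreme case under these assumptions, and a changed primary conclusion is unlikely. The issue is as-randomized validity and completeness of safety data. It should be settled before unblinding.

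**What to change.** Replace the removal sentence in 4.f with wording such as:

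> Participants who undergo CABG stay in scheduled follow-up for LDL-C, adverse events and clinical outcomes. Data collected before CABG are kept. These participants are included as randomized in the primary LDL-C analysis, with a sensitivity analysis excluding post-CABG LDL-C values. Post-CABG inflammatory-marker and PET values may be left out of the main mechanistic analyses, with the number left out reported by arm.

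The last sentence preserves the protocol's inflammation concern. It is itself an exclusion on a post-randomization event, which is why the counts by arm are needed.

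The cost is a wording change and keeping visits already scheduled for an assumed 3-9 patients. No added PET is needed. The downside is that a few LDL-C values will be measured after surgery and may be affected by it, which the sensitivity analysis examines. For the PET endpoint, the new wording would retain more data than the present one if removal was meant to cover scans already obtained.
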